8.10.2 Concomitant Procedures

A concomitant procedure is any therapeutic intervention (e.g., surgery/biopsy, physical therapy) or diagnostic assessment (e.g., blood gas measurement, bacterial cultures) performed between signing of informed consent and the final post-treatment visit.

8.11 Treatment Compliance

Compliance with treatment dosing is to be monitored and recorded by Study Center staff.

The Study Center staff is required to document the receipt, dispensing, and return of ISIS 420915 supplies. Patients who self-administer ISIS 420915 at home must record treatment in a provided dosing diary that will be reviewed by the Study Center staff and monitor.

9. SERIOUS AND NON-SERIOUS ADVERSE EVENT REPORTING

9.1 Sponsor Review of Safety Information

Safety information will be collected, reviewed, and evaluated by the Sponsor in accordance with the Safety Management Plan throughout the conduct of the clinical trial.

9.2 Regulatory Requirements

The Sponsor is responsible for regulatory submissions and reporting to the Investigators of serious adverse events (SAEs) including suspected unexpected serious adverse reactions (SUSARs) per the International Conference on Harmonization (ICH) guidelines E2A and ICH E6. Country-specific regulatory requirements will be followed in accordance with local country regulations and guidelines.

IECs/IRBs will be notified of any SAE according to applicable regulations. The DSMB will be notified of any SAE as specified in the DSMB charter.

The Sponsor will evaluate the available information and decide if there is a reasonable possibility that ISIS 420915 caused the AE and, therefore, meets the definition of a SUSAR.

For ISIS 420915 "expected" events, refer to the Investigator Brochure.

9.3 Definitions

9.3.1 Adverse Event

An adverse event is any unfavorable and unintended sign (including a clinically-significant abnormal laboratory finding, for example), symptom, or disease temporally associated with the study or use of investigational drug product, whether or not the AE is considered related to the investigational drug product.

9.3.2 Adverse Reaction and Suspected Adverse Reaction

An adverse reaction is any adverse event caused by ISIS 420915.

A suspected adverse reaction is any adverse event for which there is a reasonable possibility that ISIS 420915 caused the adverse event. A suspected adverse reaction implies a lesser degree of certainty about causality than an adverse reaction.

9.3.3 Serious Adverse Event (SAE)

A serious adverse event is any adverse event that in the view of either the Investigator or Sponsor, meets any of the following criteria:

- · Results in death
- Is life threatening: that is, poses an immediate risk of death at the time of the event
- An AE or suspected adverse reaction is considered "life-threatening" if, in the view of
 either the Investigator or Sponsor, its occurrence places the patient at immediate risk of
 death. It does not include an AE or suspected adverse reaction that, had it occurred in a
 more severe form, might have caused death

- Requires inpatient hospitalization or prolongation of existing hospitalization
- Hospitalization is defined as an admission of greater than 24 hours to a medical facility and does not always qualify as an AE.
- Results in a persistent or significant incapacity or substantial disruption of the ability to conduct normal life functions
- Results in congenital anomaly or birth defect in the offspring of the patient (whether the patient is male or female)
- Important medical events that may not result in death, are not life-threatening, or do not require hospitalization may also be considered serious when, based upon appropriate medical judgment, they may jeopardize the patient and may require medical or surgical intervention to prevent 1 of the outcomes listed in this definition. Examples of such medical events include allergic bronchospasm requiring intensive treatment in an emergency room or at home, blood dyscrasias or convulsions that do not result in inpatient hospitalization, or the development of drug dependency or drug abuse.

9.4 Monitoring and Recording Adverse Events

Any pre-existing conditions or signs and/or symptoms present in a patient prior to the start of the study (i.e., before informed consent) should be recorded as Medical History and not recorded as AEs unless the pre-existing condition worsened. The exception is AEs from the parent study (ISIS 420915-CS2) that are ongoing at the time the patient enters this study. These should be recorded as ongoing AEs from ISIS 420915-CS2. The Investigator should always group signs and symptoms into a single term that constitutes a **single unifying diagnosis** if possible.

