2.3.4 Clinical Experience

Two (2) clinical studies have been conducted with ISIS 420915; ISIS 420915-CS1 which is complete and ISIS 420915-CS2 which is ongoing. Detailed information concerning the ISIS 420915-CS1 and ISIS 420915-CS2 studies can be found in the Investigator's Brochure. A summary of each study is included below.

ISIS 420915-CS1 was a Phase 1 double-blind, placebo-controlled, dose escalation study designed to assess the safety, tolerability, pharmacokinetics, and pharmacodynamics of single and multiple doses of ISIS 420915 administered by subcutaneous injection to healthy subjects. The study enrolled 65 healthy volunteers (16 in the single dose cohorts and 49 in the multiple dose cohorts). Four (4) single dose levels (50, 100, 200, and 400 mg) and 5 multiple dose levels (50, 100, 200, 400 and 300 mg) were evaluated sequentially in the order listed. Subjects enrolled in the multiple-dose cohorts received a total of 6 doses of Study Drug administered by subcutaneous (SC) injection: 3 doses on alternate days during the first week (Days 1, 3, and 5) and then once a week for the next 3 weeks (Days 8, 15, and 22).

ISIS 420915 was well-tolerated at the dose levels and dose regimens tested in ISIS 420915-CS1. There were no serious adverse advents (SAEs). Two (2) discontinuations were considered possibly related to ISIS 420915 by the Sponsor, 1 due to constitutional symptoms (400 mg subject) and 1 due to injection site reactions (300 mg subject). The main safety findings included; 1) mild injection site reactions characterized most often by pain and erythema, 2) transient C-reactive protein elevations, primarily associated with the first injection and not associated with symptoms, and 3) retinol reductions below the lower limit of normal (LLN) which were asymptomatic and an expected consequence of transthyretin reduction.

Plasma transthyretin levels were evaluated in all cohorts and dose-dependent reductions were observed after both single and multiple-dose administration. In the multiple-dose cohorts, the mean percent reductions in transthyretin were -8%, -22%, -53%, -75% and -76% in the 50, 100, 200, 300, and 400 mg cohorts, respectively. The therapeutic goal for ISIS 420915 is to reduce transthyretin levels as much as possible at a dose level that will not cause unacceptable toxicity. Therefore, the 300 mg dose level which gave similar transthyretin reductions as the 400 mg dose level, was selected for the ISIS 420915-CS2 Phase 2/3 study.

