3.3.2.2 Other Adverse Events of Interest

The following list includes other adverse events that have been identified to be of interest:

Other AEs of interest	Definition
Coagulation abnormalities	AE with HLT: Coagulopathies
Abnormal liver function	AE within the SMQ: Drug related hepatic disorders - comprehensive search
Adverse events at the injection	AE with HLT: Injection site reaction; or
site	AE within HLT: Administration site reaction NEC.
Flu-like symptoms	AE with PT: Influenza like illness; or

Other AEs of interest	Definition	
	AEwith PT: Pyrexia (or Feeling hot or Body temperature increased) plus at least one of the following symptoms:	
CNS disorders	AE within System Organ Class (SOC): Nervous system disorder	
Haemorrhages	AE within the SMQ: Heamorrhages	
Potential complement activation	AE within SMQ: Hypersensitivity	
Reduced thryroxine	AE within SMQ: Hypothyroidism	

Results by type of haemorrhagic eventsmay be provided; the type of haemorhagic events and respective definitions will be pecified prior to database lock.

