3.3.2.3 Local Cutaneous Reactions at Injection Site {LCRIS}

The following MedDRA preferred terms are determined by the Sponsor's Pharmacovigilance personnel to represent the local cutaneous reaction at the injection site:

- Injection site erythema
- Injection site swelling
- Injection site pruritus
- Injection site pain
- Injection site tenderness

Only events that start on the day of injection and persist for at least two days, i.e. event onset date on the day of injection and resolution date not on the day of injection or the day after the injection, will be included. Events with onset date on the day of injection and missing resolution date will also be included. AEs with partial or missing dates will be handled as follows. First establish whether the event is treatment emergent (Details of TEAE definition see section 3.3.2.6 for TEAE occurred during the OLE study and section 3.3.2.7 for TEAE for overall including the parent study and OLE study). If yes, then establish if the preferred terms match the ones listed in the LCRIS definition. If yes, check whether the event onset dates are within the specified time frame. If at this stage, onset date is

missing or partially missing, the event will be considered to have started within the required time frame.

The number and percent of patients in each treatment group of the parent study experiencing LCRIS will be tabulated.

Percentage of injections leading to local cutaneous reactions at the injection site will also be summarized. Percentage of injections leading to local cutaneous reactions will be calculated for each patient as (A/B)*100, where A is the number of injections with a local cutaneous reaction at the injection site, and B is the total number of injections.

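### Protocol 9.4 asks sites to group signs into one unifying diagnosis where possible, but SAP 3.3.2.3 counts injection-site reactions (LCRIS) only under five single-sign terms, so a grouped reaction can go uncounted

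*Combined protocol and SAP*

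**What the plan says.** Protocol 9.4 (Monitoring and Recording Adverse Events) instructs: "The Investigator should always group signs and symptoms into a single term that constitutes a" unifying diagnosis, and qualifies this with a condition of feasibility. Injection-site signs are not exempted.

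SAP 3.3.2.3 defines LCRIS through a closed list of MedDRA preferred terms "determined by the Sponsor's Pharmacovigilance personnel to represent the local cutaneous reaction at the injection site". The list opens with "Injection site erythema" and continues with swelling, pruritus, pain and tenderness. An event must also begin on an injection day and still be present beyond the following day; a missing resolution date also qualifies. For events with partial or missing dates, the section sets out steps, one of which is: "If yes, then establish if the preferred terms match the ones listed in the LCRIS definition".

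Two outputs use this definition: the number and percentage of patients with LCRIS, and each patient's percentage of injections leading to LCRIS, (A/B) × 100. SAP 3.3.2.6 and 3.3.2.7 call for LCRIS in the extension-study and longitudinal analyses respectively. SAP 9.1, which removes some analyses from the final report, does not remove LCRIS.

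Separately, SAP 3.3.2.2 has a broader category of adverse events at the injection site. Its definition begins "AE with HLT: Injection site reaction; or" and goes on to a second higher level term.

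**The concern.** The recording rule and the counting rule pull in different directions. One asks for signs to be combined where possible; the other recognises only uncombined signs. Multi-sign reactions are plausible with this drug: Protocol 2.3.4 summarises the Phase 1 findings as "mild injection site reactions characterized most often by pain and erythema", and itself uses the umbrella label.

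Safety and tolerability is the primary objective, and LCRIS is one of its named tolerability summaries. If grouped reactions drop out, the per-injection percentage can be too low. Two sites seeing the same reactions can also contribute different LCRIS rates because one groups signs and the other does not.

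The neighbouring section makes the gap visible. The flu-like reaction list in SAP 3.3.2.4 contains a unifying term, influenza-like illness, as well as symptom combinations. The LCRIS list has no counterpart, and the SAP gives no reason for the difference.

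**Working it through.** The plan states no LCRIS rate and no sample-size or power figure that bears on this, so there is nothing to reproduce. The check is a trace of one event, followed by arithmetic on assumed values.

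**Trace.** Take erythema, swelling and pain that start on the injection day and last three days.

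| Step | Signs recorded separately | Grouped and coded to 'Injection site reaction' |
|---|---|---|
| Consistent with Protocol 9.4? | Yes, if the investigator sees no unifying diagnosis | Yes |
| Term among the five in SAP 3.3.2.3? | Yes | No |
| Onset and persistence rules met? | Yes | Yes |
| Patient counted as LCRIS? | Yes | Not from this event |
| Injection added to A? | Yes | No |
| In the SAP 3.3.2.2 category? | Expected | Expected |
| In the general TEAE tables? | Yes | Yes |

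The clinical event and its timing are the same in both columns. Only the recording differs.

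**Per-injection percentage.** Let g be the share of qualifying injections whose only record is a grouped, unlisted term. Then

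reported percentage = true percentage × (1 − g).

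Both g and the true rate of 10% are assumptions; the documents give neither.

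- g = 20%: 10% × 0.8 = 8%
- g = 50%: 10% × 0.5 = 5%
- g = 80%: 10% × 0.2 = 2%

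**Patient count.** This factor does not carry over. Treatment can run to 260 weekly injections (Protocol 3.4.2), and one listed-term event puts a patient in the numerator. A patient is missed only if every qualifying reaction was recorded under an unlisted term. As an illustration, assume 27 of 135 patients (20%) truly had a qualifying reaction.

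- One third have only grouped records: 27 − 9 = 18, and 18/135 = 13.3%
- Two thirds have only grouped records: 27 − 18 = 9, and 9/135 = 6.7%

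The 135 is the approximate number eligible in Protocol 3.3. The 27 and the fractions are assumed.

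**The case against.** The strongest reply is that Protocol 9.4 asks for a unifying diagnosis, and only where possible. Pain and redness at an injection site are local signs, and 'injection site reaction' is arguably a collective label rather than a diagnosis. A site that records the signs separately may be fully compliant. This stands. A reader might infer that sites following Protocol 9.4 go uncounted while sites ignoring it are counted. The documents do not support that: the wording leaves discretion, and a compliant site records a single-sign reaction under a listed term anyway.

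Second, no document says how a grouped reaction is worded or coded. The term 'Injection site reaction' is inferred from the higher level term in SAP 3.3.2.2 and the narrative in Protocol 2.3.4. A grouped record coded to one of the five terms would still count. This also stands, so the tempting conclusion that every reaction with two or more signs is lost is not supported.

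Third, the sentence requiring that terms "then establish if the preferred terms match the ones listed in the LCRIS definition" belongs to the handling of partial or missing dates and is not a general gate. That is correct, but the five-term list itself defines LCRIS for all events, so the trace is unchanged.

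Fourth, the SAP reports in two tiers, and LCRIS is meant to be the narrow one. A grouped event should remain visible in the broad tier and in the general tables, so no safety event disappears. This answers any claim of lost safety data. It does not repair LCRIS, because the broad category applies neither the onset nor the persistence rule and gives no per-injection percentage.

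**Conclusion.** The mismatch is real and limited. A multi-sign reaction that is recorded once and coded to a unifying term outside the list is not counted as LCRIS, whatever its onset and duration. The per-injection percentage can be understated as a result, and the patient count to a lesser degree. Both can reflect site recording habit as well as tolerability. Reactions with a single sign, or with signs recorded separately, are unaffected.

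A reader might take the scaled percentages above as an estimate of bias, or conclude that LCRIS is known to be biased low. Neither follows. The documents give no LCRIS rate, no share of grouped records and no evidence on site practice, so the size cannot be derived and could be small.

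The conclusion rests on two assumptions: that some sites group injection-site signs, and that some grouped records are coded outside the five terms. SAP 9.2.2 also refers some combined parent-and-extension outputs to a separate ISS SAP that was not available and might define LCRIS differently. The analyses are descriptive, with no formal hypotheses (SAP 1.3), so what is at stake is the accuracy of a tolerability summary.

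**What to change.** In SAP 3.3.2.3:

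- Add the preferred term 'Injection site reaction' to the LCRIS list, under the existing day-of-injection onset and two-day persistence rules and the same handling of incomplete dates. The documents show this name only at the higher level, so confirm the term against the MedDRA version used.
- State that an injection counts once in A, however many terms are recorded for it.
- Present LCRIS with and without the added term. The five-term definition then stays visible, and the gap between the two results shows how much recording practice matters.

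Do not import a whole higher level term from SAP 3.3.2.2. Two are named there, and either would bring in terms outside the chosen cutaneous list and largely turn LCRIS into the broad category with a timing rule. Amending Protocol 9.4 is not a useful alternative, because it would not correct events already recorded.

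The cost is a short SAP edit, one term in the programmed list and one extra tabulation. The reported LCRIS rate may rise.

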9.4.1 Serious Adverse Events

In the interest of patient safety, and to fulfill regulatory requirements, all SAEs (regardless of their relationship to ISIS 420915) should be reported to the Sponsor or designee within 24 hours of the Study Center's first knowledge of the event. The collection of SAEs will begin after the patient signs the informed consent form and stop at the end of the patient's follow-up period, which is defined as the final post-treatment visit. When the Investigator is reporting by telephone, it is important to speak to someone in person versus leaving a message. An Initial Serious Adverse Event Form should be completed and a copy should be faxed to the Sponsor or designee.

Detailed information should be actively sought and included on Follow-Up Serious Adverse Event Forms as soon as additional information becomes available. All SAEs will be followed until resolution. SAEs that remain ongoing past the patient's last protocol-specified follow-up visit will be evaluated by the Investigator and Sponsor. If the Investigator and Sponsor agree the patient's condition is unlikely to resolve, the Investigator and Sponsor will determine the follow-up requirement.

9.4.2 Non-Serious Adverse Events

The recording of non-serious AEs will begin after the patient signs the informed consent form and will stop at the end of the patient's follow-up period, which is defined as the final post-treatment visit. The Investigator will monitor each patient closely and record all observed or volunteered AEs on the Adverse Event CRF.

9.4.3 Evaluation of Adverse Events (Serious and Non-Serious)

The Investigator's opinion of the following should be documented in the Adverse Event eCRF:

9.4.3.1 Relationship to ISIS 420915

The event's relationship to ISIS 420915 is characterized by 1 of the following:

- **Related:** There is clear evidence that the event is related to the use of ISIS 420915, e.g., confirmation by positive re-challenge test.
- **Possible:** The event cannot be explained by the patient's medical condition, concomitant therapy, or other causes, and there is a plausible temporal relationship between the event and ISIS 420915 administration.
- Unlikely/Remote: An event for which an alternative explanation is more likely (e.g., concomitant medications or ongoing medical conditions) or the temporal relationship to ISIS 420915 administration and/or exposure suggests that a causal relationship is unlikely (For reporting purposes, Unlikely/Remote will be grouped together with Not Related).
- **Not Related:** The event can be readily explained by the patient's underlying medical condition, concomitant therapy, or other causes, and therefore, the Investigator believes no relationship exists between the event and ISIS 420915.

9.4.3.2 Severity

The event's severity is characterized by 1 of the following:

- **Mild:** The event is easily tolerated by the patient and does not affect the patient's usual daily activities.
- **Moderate:** The event causes the patient more discomfort and interrupts the patient's usual daily activities.
- **Severe:** The event is incapacitating and causes considerable interference with the patient's usual daily activities.

If the event is an SAE, then all applicable seriousness criteria must be indicated (criteria listed in Section 9.3.3).

9.4.3.3 Action Taken with ISIS 420915

Action taken with ISIS 420915 due to the event is characterized by 1 of the following:

- None: No changes were made to ISIS 420915 administration and dose
- Permanently Discontinued: ISIS 420915 was discontinued and not restarted
- **Temporarily Interrupted, restarted:** Dosing was temporarily interrupted or delayed due to the AE and restarted
- Reduced dose: Dosing was reduced to a lower dose
- Reduced schedule: Dosing frequency was reduced

9.4.3.4 Treatment Given for Adverse Event

Any treatment (e.g., medications or procedures) given for the AE should be recorded in the Adverse Event eCRF (treatment should also be recorded in the concomitant treatment or ancillary procedures eCRF as appropriate).

9.4.3.5 Outcome of the Adverse Event

If the event is a non-serious AE then the event's outcome is characterized by 1 of the following:

- AE Persists: Patient terminates from the trial and the AE continues
- **Recovered:** Patient recovered completely from the AE
- **Became Serious:** The event became serious (the date that the event became serious should be recorded as the Resolution Date of that AE and the Onset Date of the corresponding SAE)
- Change in Severity (if applicable): AE severity changed

If the event is an SAE then the event's outcome is characterized by 1 of the following:

- Ongoing: SAE continuing
- **Persists (as non-serious AE):** Patient has not fully recovered but the event no longer meets serious criteria and should be captured as an AE in the non-serious AE eCRF (the SAE resolution date should be entered as the date of onset of that AE)
- **Recovered:** Patient recovered completely from the SAE (the date of recovery should be entered as the SAE resolution date)
- Fatal: Patient died (the date of death should be entered as the SAE resolution date)

9.5 Procedures for Handling Special Situations

9.5.1 Abnormalities of Laboratory Tests

Clinically-significant abnormal laboratory test results may, in the opinion of the Investigator, constitute or be associated with an AE. Examples of these include abnormal laboratory results that are associated with symptoms, or require treatment, e.g., bleeding due to thrombocytopenia, tetany due to hypocalcemia, or cardiac arrhythmias due to hyperkalemia. Whenever possible, the

underlying diagnosis should be listed in preference to abnormal laboratory values as AEs. Clinically-significant abnormalities will be monitored by the Investigator until the parameter returns to its baseline value or until agreement is reached between the Investigator and the Study Medical Monitor. Laboratory abnormalities deemed not clinically-significant (NCS) by the Investigator should not be reported as AEs. Similarly, laboratory abnormalities reported as AEs by the Investigator should not be deemed NCS on the laboratory sheet.

The Investigator is responsible for reviewing and signing all laboratory reports. The signed clinical laboratory reports will serve as source documents.

